4.7 Toxicities and Dosing Delays/Dose Modifications

Any patient who receives treatment on this protocol will be evaluable for toxicity. Each patient will be assessed for the development of toxicity according to the Time and Events table. Toxicity will be assessed according to the NCI Common Toxicity Criteria for Adverse Events (CTCAE), version 4.03. Dose adjustments should be made according to the system showing the greatest degree of toxicity.

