4.5.1 Dose modification and dose delay

4.5.1.1 Therapeutic drug monitoring: Therapeutic drug monitoring of Everolimus blood concentrations is required for patients enrolled on study and taking Everolimus. Testing is to be performed by Quest Diagnostics using a validated bioanalytical LC/MS method (test code 18883X). Trough concentrations should be assessed 2 weeks (+/- 4 days) after the initial dose, after any change in dose or formulation, after an initiation or change in co-administration of CYP3A4 inducers or inhibitors, or after any change in hepatic status.

4.5.1.2 Dosing modifications:

Titrate the dose to attain trough concentrations of 5 to 15 ng/mL.

- For trough concentrations less than 5 ng/mL, increase the daily dose by 2 mg and repeat trough concentration in 2 weeks (+/- 4 days).
- For trough concentrations greater than 15 ng/mL, reduce the daily dose by 2 mg and repeat trough concentration in 2 weeks (+/- 4 days).
- The lowest possible dose level of Everolimus is 2 mg daily.
- If dose reduction is required for patients receiving the lowest available strength, administer every other day.

- For patients who do not tolerate the protocol-specified dosing schedule, dose adjustments are permitted in order to allow the patient to continue the study treatment. Dose levels are as follows: Level -2 = 3 mg/m²/dose, Level -1 = 3.8 mg/m²/dose, Level 0 = 4.5 mg/m²/dose, Level +1 = 5.2 mg/m²/dose and Level +2 = 6 mg/m²/dose. If dose adjustments need to be made for toxicity, patients' doses of Everolimus should not be targeted to achieve a trough level of 5 – 15 ng/mL.

Table 4-1**Dosing guidelines for Everolimus-related non-hematologic toxicities**

Toxicity	Action
Non-Infectious Pneumonitis	Please refer to Table 4-3.
Reactivation of HBV or HCV flare	Please refer to Table 4-5.
AST or ALT elevation	Maintain current dose level
Grade 1 (> ULN - 3.0 x ULN)	
Grade 2 (> 3.0 - 5.0 x ULN)	
AST or ALT elevation Grade 3 (> 5.0 - 20.0 ULN)*	Interrupt Everolimus administration until resolution to ≤ grade 1 (or ≤ grade 2 if baseline values were within the range of grade 2). If resolution occurs ≤ 7 days, Everolimus should be re-started at the dose level prior to interruption. If resolution takes > 7 days, or if event recurs within 28 days, hold Everolimus until recovery to ≤ grade 1 or baseline grade / value and reintroduce Everolimus at one dose level lower, if available.

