AST or ALT elevation Grade 4 (> 20 x ULN)*	Interrupt Everolimus administration until resolution to ≤ grade 1 (or ≤ grade 2 if baseline values were within the range of grade 2). If resolution occurs ≤ 7 days, Everolimus should be re-started at one dose level lower. If resolution takes > 7 days, discontinue Everolimus.
Recurrence of Grade 4 AST or ALT elevation after dose reduction or toxicity requiring Everolimus interruption for > 28 days	Discontinue Everolimus.
Intolerable grade 2 mucositis, or grade 3 AE, except hyperglycemia or hypertriglyceridemia or hypercholesterolemia	Interrupt Everolimus administration until resolution to ≤ grade 1 or baseline grade / value. If resolution occurs within ≤ 7 days, Everolimus should be re-started at the dose level prior to interruption. If resolution takes > 7 days, or if event recurs within 28 days, hold Everolimus until recovery to ≤ grade 1 or baseline grade / value and reintroduce Everolimus at one dose level lower, if available. Patients will be withdrawn from the study if they fail to recover to ≤ grade 1 or baseline grade / value within 28 days.
Any other grade 4	Hold Everolimus until recovery to grade ≤ 1 or baseline value Reintroduce Everolimus at one dose level lower, if available.
Grade 3 or 4 clinical liver failure (asterixis or encephalopathy/coma)	Discontinue Everolimus
Recurrence of intolerable grade 2 mucositis or grade 3 event after dose reduction	Reduce dose to the next lower dose level, if available. The lowest possible dose level of Everolimus is 2 mg daily. Below this level, Everolimus must be discontinued.
Recurrence of grade 4 after dose reduction	Discontinue Everolimus
Any non-hematologic toxicity requiring Everolimus interruption for > 28 days	Discontinue Everolimus

* Should HCV flare be confirmed, the guidelines for flare must take precedence (Table 4-4).

Table 4-2**Dosing guidelines for Everolimus-related hematologic toxicities**

Toxicity	Action
Grade 2 thrombocytopenia (platelets <75, \geq 50x109/L)	Interrupt Everolimus until resolution to grade \leq 1 If resolution occurs \leq 7 days, reintroduce Everolimus at the dose level prior to interruption. If resolution occurs $>$ 7 days, or event occurs within 28 days, reintroduce Everolimus at one dose level lower, if available.

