4.5.9 Management of hepatitis reactivation / flare

Reactivation of Hepatitis B (HBV) has been observed in patients with cancer receiving chemotherapy.³² Sporadic cases of Hepatitis B reactivation have also been seen in this setting with everolimus. Use of antivirals during anti-cancer therapy has been shown to reduce the risk of Hepatitis B virus reactivation and associated morbidity and mortality.³³ A detailed assessment of Hepatitis B/C medical history and risk factors must be done for all patients at screening, with testing performed prior to the first dose of everolimus.

4.5.10 Monitoring and prophylactic treatment for hepatitis B reactivation.

Table 4-4 provides details for monitoring and prophylactic therapy according to the screening results of viral load and serologic markers testing.

Table 4-4 Action to be taken based on screening hepatitis B results

Test	Result	Result	Result	Result	Result
HBV-DNA	+	+ or -	-	-	-
HBsAg	+ or -	+	-	-	-
HBsAb	+ or -	+ or -	+ and no prior HBV vaccination	+ or -	- or + with prior HBV vaccination
HBcAb	+ or -	+ or -	+ or -	+	-
Recommendation	Prophylaxis treatment should be started 1-2 weeks prior to first dose of Everolimus Monitor HBV-DNA approximately every 4-8 weeks		No prophylaxis Monitor HBV-DNA approximately every 3-4 weeks		No specific action

Antiviral prophylaxis therapy should continue for at least 4 weeks after last dose of Everolimus. For HBV reactivation definition and management guidelines, see Table 4-5.

Table 4-5 Guidelines for the management of hepatitis B reactivation

HBV reactivation (with or without clinical signs and symptoms)*	
For patients with baseline results: Positive HBV-DNA OR positive HBsAg ----- reactivation is defined as: [Increase of 1 log in HBV-DNA relative to baseline HBV-DNA value OR new appearance of measurable HBV-DNA]	Treat: Start a second antiviral medication AND Interrupt Everolimus administration until resolution: • \leq baseline HBV-DNA levels If resolution occurs within \leq 28 days, Everolimus should be re-started at one dose lower, if available. If the patient is already receiving the lowest dose of Everolimus according to the protocol, the patient should restart at the same dose after resolution. Both antiviral therapies should continue at least 4 weeks after last dose of Everolimus. If resolution occurs $>$ 28 days Patients should discontinue Everolimus but continue both antiviral therapies at least 4 weeks after last dose of Everolimus.

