4.5.11 Monitoring for hepatitis C flare

The following two categories of patients should be monitored every 4–8 weeks for HCV flare:

- Patients with detectable HCV RNA-PCR test at screening.
- Patients known to have a history of HCV infection, despite a negative viral load test at screening (including those that were treated and are considered 'cured')

For definitions of HCV flare and actions to be taken in the event of a flare, please refer to
Table 4-6.

Table 4-6**Guidelines for the management of hepatitis C flare**

Baseline results	HCV flare definition*	HCV flare management
Detectable HCV-RNA	> 2 log ₁₀ IU/mL increase in HCV-RNA AND ALT elevation > 5 x ULN or 3 x baseline level, whichever is higher.	Discontinue Everolimus
Knowledge of past hepatitis C infection with no detectable HCV-RNA	New appearance of detectable HCV-RNA AND ALT elevation > 5 x ULN or 3 x baseline level, whichever is higher.	Discontinue Everolimus

* All flares of HCV are to be recorded as grade 3 (e.g. CTCAE Version 4.03 - Investigations - Other: Viral Flare), unless considered life threatening by the investigator; in which case they should be recorded as grade 4. Date of viral flare is the date on which both the clinical criteria described above were met. (e.g., for a patient whose HCV-RNA increased by 2 logs on 01 JAN 2011 and whose ALT reached > 5 x ULN on 22 JAN 2011, the date of viral flare is 22 JAN 2011).

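### Table 4-1 sends hepatitis C flare to two hepatitis B tables instead of Table 4-6, which requires everolimus to be discontinued

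*Combined protocol and SAP*

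**What the plan says.** Table 4-1 in section 4.5.1.2 mentions HCV flare twice.

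- A row labelled "Reactivation of HBV or HCV flare" gives no action of its own and refers the site to Table 4-5.
- A footnote to the grade 3 and grade 4 AST/ALT rows reads "Should HCV flare be confirmed, the guidelines for flare must take precedence (Table 4-4").

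Sections 4.5.10 and 4.5.11 contain the three hepatitis tables.

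- Table 4-4 is titled "Action to be taken based on screening hepatitis B results". It covers antiviral prophylaxis and HBV-DNA monitoring.
- Table 4-5 is titled "Guidelines for the management of hepatitis B reactivation". It defines events by HBV-DNA, interrupts treatment and, if the event resolves within 28 days, says "Everolimus should be re-started at one dose lower, if available".
- Table 4-6 is titled "Guidelines for the management of hepatitis C flare". It requires discontinuation in both of its baseline categories. Section 4.5.11 introduces it with "For definitions of HCV flare and actions to be taken in the event of a flare, please refer to" Table 4-6.

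Separately, section 4.7 names CTCAE version 4.03 as the toxicity scale and then says "Dose adjustments should be made according to the system showing the greatest degree of toxicity".

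**The concern.** Table 4-1 is operative dosing text. A site managing a child with raised transaminases works from its AST/ALT rows and their footnote. The footnote rightly says that the flare guideline overrides those rows, but it names a table with nothing on HCV. The row meant for HCV flare leads to a hepatitis B table under which treatment can resume. At stake is whether everolimus is restarted after an event for which the protocol requires it to stop.

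The sentence in 4.7 raises a lesser question. It does not say what happens when two toxicities in different systems call for different actions or different recovery grades.

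**Working it through.** No sample size or power figure bears on this, so the check sets the texts side by side.

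**Step 1: trace each explicit HCV-flare pointer.**

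| Where | Points to | What that table covers | Correct for HCV? |
|---|---|---|---|
| Table 4-1, joint HBV/HCV row | Table 4-5 | Hepatitis B reactivation | No |
| Table 4-1, AST/ALT footnote | Table 4-4 | Hepatitis B screening actions | No |
| Section 4.5.11 | Table 4-6 | Hepatitis C flare | Yes |

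Two of three are wrong, including both in Table 4-1. Table 4-5 is the right target for the HBV part of the joint row; only the HCV part is misdirected.

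**Step 2: does every flare reach a footnoted row?** Table 4-6 requires ALT above the higher of 5 × ULN and 3 × baseline. Section 3.1.4.2 caps ALT at entry at 2.5 × ULN, so 3 × baseline is at most 3 × 2.5 = 7.5 × ULN. The flare threshold therefore lies between 5 and 7.5 × ULN. The footnoted rows cover ALT above 5 up to 20 × ULN (grade 3) and above 20 × ULN (grade 4). Every flare falls in one of them.

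**Step 3: compare the resulting actions.**

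| Rule applied | ALT > 5 to 20 × ULN | ALT > 20 × ULN |
|---|---|---|
| AST/ALT row, resolved in ≤ 7 days | Restart, same dose level | Restart, one level lower |
| AST/ALT row, resolved in > 7 days | Restart, one level lower, unless held > 28 days | Discontinue |
| Table 4-5, if borrowed | Restart one dose lower if resolved in ≤ 28 days | Same |
| Table 4-6 (correct) | Discontinue | Discontinue |

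Three of the four AST/ALT cells allow a restart. Under Table 4-6 none does.

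**Step 4: who could be affected?** Section 3.2.5.5 excludes chronic hepatitis. Section 4.5.11 nevertheless plans monitoring for patients with detectable HCV RNA at screening or a history of HCV infection, so the protocol allows for such patients. It gives no HCV rate, so no expected number among the 18 can be stated.

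**Step 5: the sentence in 4.7.** Coming straight after the CTCAE reference, the greatest degree most naturally means the highest grade. Whether a dose adjustment includes an interruption is unclear. Section 4.5.2 and the last column of Table 4-3 use the term broadly enough to include it. Section 4.5.1.2 uses it for dose levels, and section 7.2.1 lists an adjusted dose separately from interruption and discontinuation. Section 4.7 cancels no row of any table. The text therefore also allows a reading in which every applicable row holds.

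**The case against.** The best defence on HCV is that a site could hardly be misled. The footnote acts only once a flare is confirmed, and a flare is defined only in Table 4-6, in the same row as the instruction to discontinue. On-treatment HCV monitoring is set up by 4.5.11, which cites Table 4-6 correctly, and 4.5.2 lists all six tables. Table 4-5 has no HCV row to apply. All of this stands. A reader might infer from Table 4-1 that sites would restart everolimus after an HCV flare; the documents do not support that as a likely outcome. What remains is that two pointers for a mandatory-stop event name the wrong tables.

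A reader might also infer that 4.7 contradicts Tables 4-1 and 4-2, because their actions do not rise with grade across systems. Two examples are tempting.

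- Grade 3 glucose or lipid events are exempt from the grade 3 interruption row, while grade 2 thrombocytopenia requires interruption. This becomes a conflict only if the exempt event is assumed to mean no change; no row assigns it an action, so it gives a site nothing to adjust by.
- Grade 3 neutropenia may resume at grade 2 or lower, or baseline, while intolerable grade 2 mucositis must reach grade 1 or lower, or baseline. This mostly disappears once toxicity is reassessed: when neutropenia has fallen to grade 2, the mucositis is at least tied for highest. Table 4-2 has no grade 2 neutropenia row, so if the mucositis is still intolerable its own row keeps the drug on hold.

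Both examples also need a reading in which one row silently cancels another mandatory one. The documents support an ambiguity in 4.7, not a contradiction.

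**Conclusion.** The HCV cross-references are wrong as written. Two of the three explicit pointers name hepatitis B tables, and every flare falls in a footnoted AST/ALT row that, without Table 4-6, would usually allow a restart. This follows from the text and needs no assumption about how often flares occur. The correction is worth making because it concerns a stop instruction in a dosing table, but the practical risk is low for the reasons given above.

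The sentence in 4.7 merits at most an optional clarification, and investigator judgment under 4.8 and 5.5 makes harm from it unlikely. Neither point changes the primary endpoint or the two-stage design.

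**What to change.** In Table 4-1, change the joint row to: *HBV reactivation: Table 4-5; HCV flare: Table 4-6.* Change the AST/ALT footnote to cite Table 4-6. These two edits fit in any protocol amendment and add no data, visits or patients.

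Optionally, replace the last sentence of 4.7 with: *When a patient has more than one toxicity, the most restrictive action required by any applicable row of Tables 4-1, 4-2, 4-3, 4-5 and 4-6 governs, and everolimus resumes only when each toxicity meets its own recovery criterion.* Table 4-4 is left out because it deals with screening and prophylaxis, not toxicity. The optional change has a cost: some holds may be longer. Holds beyond 28 days lead to discontinuation under Tables 4-1 and 4-2, and permanent discontinuations count toward the stopping rule in 7.6 (4 of the first 10 patients or 6 of the first 16).

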4.8 Duration of Therapy

In the absence of treatment delays due to adverse events, treatment may continue for 2 years or until:

- Disease progression
- Inter-current illness that prevents further administration of treatment
- Unacceptable adverse event(s)
- Patient decides to withdraw from the study, **OR**
- General or specific changes in the patient's condition render the patient unacceptable for further treatment in the judgment of the investigator.

4.9 Duration of Follow Up

Patients will be followed after removal from treatment or until death, whichever occurs first. Follow-up for survival will occur by the treating oncologist and will be communicated to the PI or designee at 6-month intervals by phone or medical record review. Patients removed from treatment for unacceptable adverse events will be followed until resolution or stabilization of the adverse event.

4.10 Removal of Patients from Protocol Therapy

Patients will be removed from therapy when any of the criteria listed in Section 5.5 apply. Notify the Principal Investigator, and document the reason for study removal and the date the patient was removed in the Case Report Form. The patient should be followed-up per protocol.

4.11 Patient Replacement

If a patient is withdrawn from the study prior to completing 1 course of therapy without experiencing a DLT prior to withdrawal, an additional patient may be added to that dose level.

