5.5 Removal of Subjects from Study

Patients can be taken off the study treatment and/or study at any time at their own request, or they may be withdrawn at the discretion of the investigator for safety, behavioral or administrative reasons. The reason(s) for discontinuation will be documented and may include:

- 5.5.1 Patient voluntarily withdraws from treatment (follow-up permitted);
- 5.5.2 Patient withdraws consent (termination of treatment and follow-up);
- 5.5.3 Patient is unable to comply with protocol requirements;
- 5.5.4 Patient demonstrates disease progression (unless continued treatment with study drug is deemed appropriate at the discretion of the investigator);
- 5.5.5 Patient experiences toxicity that makes continuation in the protocol unsafe;
- 5.5.6 Treating physician judges continuation on the study would not be in the patient's best interest;

- 5.5.7 Patient becomes pregnant (pregnancy to be reported along same timelines as a serious adverse event);
- 5.5.8 Development of second malignancy (except for basal cell carcinoma or squamous cell carcinoma of the skin) that requires treatment, which would interfere with this study;
- 5.5.9 Lost to follow-up: If a research subject cannot be located to document survival after a period of 2 years, the subject may be considered "lost to follow-up." All attempts to contact the subject during the two years must be documented and approved by the Data Monitoring Committee.

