6.0 MEASUREMENT OF EFFECT

6.1 Response Assessment

6.1.1 Definitions

Evaluable for toxicity. All patients will be evaluable for toxicity from the time of their first treatment with study drug.

Evaluable for objective response. Only those patients who have measurable disease present at baseline, have received at least one cycle of therapy, and have had their disease re-evaluated will be considered evaluable for response. These patients will have their response classified according to the definitions stated below. (Note: Patients who exhibit objective disease progression prior to the end of cycle 1 will also be considered evaluable.)

In this study, response and progression will be evaluated using the International Society of Pediatric Oncology Brain, Tumor Subcommittee for the Reporting of Trials criteria shown below with slight modification.³⁴ Response will be assessed by magnetic resonance imaging (MRI) scan every 8 weeks (every 2 cycles) for 1 year, then every 12 weeks.

6.1.2 Complete Response (CR):

Complete disappearance on MRI of all enhancing tumor and mass effect, on a stable or decreasing dose of corticosteroids (or receiving only adrenal replacement doses), accompanied by a stable or improving neurologic examination and must be sustained for at least 4 weeks. If cerebral spinal fluid (CSF) evaluation was positive, it must become negative. CSF negativity has to be confirmed at least two times at consecutive samplings if the CSF was positive.

6.1.3 Partial Response (PR):

Greater than or equal to 50% reduction in tumor size by bi-dimensional measurement on a stable or decreasing dose of corticosteroids, accompanied by a stable or improving neurologic examination and must be sustained for at least 4 weeks.

6.1.4 Minor Response (MR):

Greater than or equal to 25% to < 50% reduction in tumor size by bi-dimensional measurement on a stable or decreasing dose of corticosteroids, accompanied by a stable or improving neurologic examination and must be sustained for at least 4 weeks.

6.1.5 Stable Disease (SD):

Neurologic examination is at least stable and maintenance corticosteroid dose is not increased, and MRI meets neither the criteria for MR nor the criteria for progressive disease and must be sustained for at least 8 weeks.

6.1.6 Stable Disease (SD):

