9.2 Sample Size and Accrual

Simon's two-stage optimal design³⁵ is used to compute the number of patients to be recruited for this phase II trial. The null hypothesis that the true objective response rate (ORR) is 10% will be tested against a one-sided alternative. In the first stage, 7 patients will be accrued. If there is no ORR seen in these 7 patients, the study will be stopped.

Otherwise, 11 additional patients will be accrued for a total of 18 patients. The null hypothesis will be rejected if 4 or more ORRs are observed in 18 patients. This design yields a type I error rate of 10% and power of 80% when the true ORR is 30%. It is expected that the accrual will be completed in 2 years since 9 patients are expected to be recruited in a year.

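### Section 4.11 allows replacement of a child who progresses in course 1, whom section 6.1.1 counts as evaluable; used that way, it can push the type I error above the stated 10%

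*Combined protocol and SAP*

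**What the plan says.** All references are to the combined protocol and SAP.

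- **Section 4.11** sets the replacement condition: "If a patient is withdrawn from the study prior to completing 1 course of therapy without experiencing a DLT prior to withdrawal". When it is met, "an additional patient may be added to that dose level". No reason for withdrawal is excepted.
- **Sections 4.10 and 5.5.** Section 4.10 sends removals to the list in section 5.5, where item 5.5.4 reads "Patient demonstrates disease progression", subject to the investigator's discretion to continue treatment.
- **Section 6.1.1** limits response evaluation to patients with measurable baseline disease, at least one cycle and a re-evaluation. It then adds: "Patients who exhibit objective disease progression prior to the end of cycle 1 will also be considered evaluable". Section 6.1.7 repeats the one-cycle condition without that addition.
- **Sections 2.3 and 9.1** define ORR as CR, PR and prolonged stable disease together. Both also list dose-limiting toxicities as an endpoint, without criteria or an observation window.
- **Section 4.5.1.2** lists dose levels -2 to +2 for adjusting an individual patient's dose.
- **Section 9.2** sets stage 1 at 7 patients, with this futility rule: "If there is no ORR seen in these 7 patients, the study will be stopped". With at least one response, stage 2 adds 11, and 4 or more responses among 18 reject the null hypothesis.
- **Section 6.1.9** holds a second replacement rule, for patients removed when central MRI review disagrees with the local reading.

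**The concern.** A child who progresses in the first four weeks without a DLT meets the wording of 4.11 and can be replaced. Under 6.1.1 the same child, if the progression is objective, is evaluable and cannot be a responder. The plan does not say which provision governs the count.

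The rule reads like one written for dose escalation. This trial has a single arm and one starting dose, so no cohort exists at a dose level to be refilled. Because DLT has no criteria, whether a given early stop meets the condition is a matter of judgement. Because the rule is permissive and the trial is open label, that judgement can be made after the outcome is known.

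Early progression is direct evidence against activity. Replacing such children selectively removes failures, or adds further chances of a response against an unchanged cut-off. With decision rules of 0 of 7 and 4 of 18, one or two children are enough to matter.

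**Working it through.** **Inputs from section 9.2.** Null ORR 10%, one-sided; alternative 30%; stage 1 n = 7, stop at 0 responses; total n = 18, reject at 4 or more; stated type I error 10% and power 80%.

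**Input not in the documents.** The share q of children who progress in course 1 and are replaced. I assume 5% to 20%.

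**Step 1: the plan's own figures.** With X1 ~ Bin(7, p) and X2 ~ Bin(11, p),

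P(reject) = Σ over x = 1 to 7 of P(X1 = x) × P(X2 ≥ 4 − x).

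At p = 0.10:

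| x | P(X1 = x) | P(X2 ≥ 4 − x) | product |
|---|---|---|---|
| 1 | 0.3720 | 0.0896 | 0.0333 |
| 2 | 0.1240 | 0.3026 | 0.0375 |
| 3 | 0.0230 | 0.6862 | 0.0158 |
| 4 to 7 | 0.0027 | 1 | 0.0027 |

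The sum is 0.0893. At p = 0.30 the same formula gives 0.8000. The chance of stopping at stage 1 under the null is 0.9^7 = 0.478. A grid search for Simon's optimal design with these inputs returns the same 0/7 and 3/18 boundaries. The stated design is reproduced.

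**Step 2: early progressors replaced and dropped from the count.** Every child dropped is a non-responder, so the response rate among those counted is p/(1 − q). With p = 0.10:

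| q | apparent ORR 0.10/(1 − q) | type I error | stage 1 stopping probability |
|---|---|---|---|
| 0 | 10.0% | 0.089 | 0.478 |
| 5% | 10.5% | 0.103 | 0.459 |
| 10% | 11.1% | 0.120 | 0.438 |
| 15% | 11.8% | 0.140 | 0.416 |
| 20% | 12.5% | 0.165 | 0.393 |

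The stated 10% is crossed at q = 3.9%, where the apparent ORR is 0.10/0.961 = 10.4%.

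**Step 3: early progressors kept in the count and extra patients added.** If 6.1.1 is honoured and 4.11 is still used, k patients are added in stage 2 with the cut-off of 4 unchanged. Replacing 11 by 11 + k in Step 1 gives:

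| k | total counted | type I error |
|---|---|---|
| 1 | 19 | 0.103 |
| 2 | 20 | 0.117 |
| 3 | 21 | 0.131 |

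**Step 4: no replacement.** If the child fills one of the 7 or 18 places as a non-responder, Step 1 applies unchanged: 0.089 and 0.800.

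**The case against.** The best defence is textual. Section 4.11 speaks of withdrawal from the study, while 5.5 separates study treatment from study, 4.8 treats progression as ending treatment, and 4.9 and 5.3 continue follow-up. On that reading, a child off treatment for progression has not been withdrawn and 4.11 does not apply. The reading is possible, but the text does not state it: 5.5 is headed as removal from study, lists progression, and is the list 4.10 relies on.

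Second, 4.11 does not say that a replaced child leaves the denominator, and 6.1.1 keeps an objective progressor in. This stands, and it is why Step 3 is needed. A reader might take 0.165 as the trial's actual error rate. The documents do not support that, because the figure requires both an assumed 20% rate and an exclusion that 6.1.1 rules out for objective progression.

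Third, course 1 progression may be uncommon. The first scheduled on-treatment MRI is before course 3 (section 5.2.2), so it would be found clinically or on an unscheduled scan. This also stands, and the size is therefore unknown. Section 6.1.1 does, however, provide for the event, and 6.1.7 counts neurologic worsening as progression.

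Three further inferences go too far:

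- **Dose levels are undefined.** Section 4.5.1.2 defines them, but as steps within a patient.
- **Replacement hides early intolerance from the safety analysis.** Sections 4.7, 6.1.1 and 6.2 keep every treated patient evaluable for toxicity.
- **All course 1 stops belong in Step 2.** A child who stops for toxicity without progression before completing a cycle is already outside the evaluable set under 6.1.1, whatever 4.11 says.

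**Conclusion.** The point holds as a conflict in the wording that reaches the primary decision rule. Nothing in 4.11 excludes course 1 progression, 6.1.1 treats objective cases as evaluable, and 9.2 does not settle who makes up the 7 and 18.

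Using 4.11 for such children exceeds the stated 10% on either way of counting: above about 4% replaced if they are dropped, or from the first stage 2 addition if they are kept. At the low end the excess is small (0.103 against 0.10), so it would be too strong to say that the rules are invalidated. The calculations assume that every replaced child is a non-responder and that the cut-offs stay as planned. The rate of course 1 progression is an assumption throughout.

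The gap between 0.0893 and 10% is ordinary discreteness and not an error. The undefined DLT endpoint is a separate, minor point.

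**What to change.** 1. **Section 4.11:** state that a treated child who progresses or dies of disease in course 1 is not replaced and fills one of the 7 or 18 places as a non-responder. Remove the DLT and dose-level conditions.
2. **Section 9.2:** state which patients make up the 7 and the 18.
3. **Sections 4.11, 6.1.1 and 6.1.7:** say consistently how a child who stops in course 1 for toxicity without progression is counted. Counting that child as a non-responder keeps the design's error rate.
4. **Section 6.1.9:** keep the central-review replacement as an explicit, separately listed exception, reconciled with the new text. A blanket rule that only never-dosed patients may be replaced would contradict it, since 6.1.9 covers patients who have already started drug.
5. **Sections 2.3 and 9.1:** separately, define the dose-limiting toxicity endpoint or replace it with a safety measure already collected.

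The cost is an amendment to several short passages. The planned 18 stays, and the design keeps a type I error of 0.089 and power of 0.80. The reported ORR may be slightly lower than it would be with replacement.
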